Start date for all signs and symptoms (month, year)

- Diagnostic methods: TAB, High-resolution color Doppler ultrasound of the temporal arteries, MRI of the temporal arteries, 18FDG-PET, Computed tomography

angiography (CTA), Magnetic resonance angiography, signs/symptoms, erythrocyte Sedimentation Rate (ESR), C-Reactive protein (CRP), other.

○ Clinical form:

- Relapses: date (month, year), treatments and doses, criteria for identifying relapse (clinical, biological, other)
- GCs-dependence: dose of prednisone after GCA diagnosis
- Complications during the course of the disease: ischemia-related vision loss, stroke, TIA, thoracic or abdominal aortic aneurysm, other.

» GCA activity:

- Clinical signs and symptoms of GCA activity at diagnosis and at inclusion: GCA-related fever ($> 38^{\circ}\text{C}$), symptoms of PMR (morning stiffness and/or pain in the shoulder and/or pelvic girdles, inflammatory arthromyalgia, peripheral arthritis, other), localised headache, temporal artery or scalp tenderness, visual signs or symptoms (e.g. acute or subacute vision loss due to arteritic anterior ischemic optic neuropathy; A-AION), transient blurry vision (generally monocular or at least affecting one eye at a time, but potentially affecting both eyes), jaw or mouth pain, extremity claudication, other features judged by the investigator to be consistent with a GCA or PMR flare.

Start date of signs and symptoms (month, year)

» Treatments:

- Previous and on-going specific GCA treatments since diagnosis:
- GCs (start and end date, dose/day, administration route, current dose, cumulative dose, kinetic)
 - Immunosuppressants (MTX, cyclophosphamide, cyclosporine, azathioprine, mycophenolate mofetil, leflunomide, dapsone, hydroxychloroquine, other) (start and end date, dose at starting date, current dose, maximum dose)
 - Targeted biologic therapy (adalimumab, etanercept, abatacept, tocilizumab, infliximab, other) (start and end date, dose at starting date, current dose)
 - Janus Kinase inhibitors (start and end date, dose at starting date, current dose)
- Treatments at diagnosis and inclusion visit: antiplatelet agents, statins, antiosteoporotic treatments, antihypertensive (start date, treatment name).
- Other significant concomitant treatments (start and end date, indication)

- Treatments for comorbidities related to GC intake (start and end date, indication)

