The following endpoints will be described overall and by type of patient (prevalent/incident), by time between signs/symptoms and diagnosis (qualitative variable), and by type of physicians who follows the patient:

- » GCA duration
- » Initial presentation: proportions of patients with cranial GCA, PMR, extracranial GCA, ESR/CRP, general signs
- » Clinical form
 - Proportion of patients with relapse and number of relapse,
 - Proportion of patients with recurrence and number of recurrences,
 - Dose of GCs-dependence
 - Proportion of patients with GCA complications.

Analysis of potential factors associated to relapse will be performed using logistic regression. The associated factors will be defined in the SAP.

- » GCA activity
 - Proportions of each clinical signs/symptoms of GCA activity

- Scores of the patient and physician global arteritis activity VAS (quantitative variable)

The concordance between the scores of the patient and physician global arteritis activity VAS will be evaluated using the kappa coefficient.

The potential factors associated with the increase of the global arteritis activity will be studied.

Description of the health status of GCA patients

» SF-36 questionnaire

The SF-36 is a self-report, 36 item survey measuring health-related quality-of-life. The SF-36 consists of eight scaled scores. A score ranging from 0 (indicating the worse health status) to 100 (indicating the best health status) is assigned for each domain. Scores and missing data of the SF-36 were handled according to the user's manual. The score for each item of SF-36 will be presented (in quantitative) as well as the total score for each domain.

» EQ5D-3L questionnaire

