5.5.2 Description of GCA characteristics

First the following parameters will be presented:

- Time between diagnosis and inclusion will be described as quantitative variable (months) ([APPENDIX](#))
- Type of patient
 - Proportion of incident patients (newly diagnosed): patients with a diagnosis of GCA \leq 6 weeks from inclusion
 - Proportion of prevalent patients (not newly diagnosed): patients with a diagnosis of GCA $>$ 6 weeks from inclusion.

Then the following endpoints will be described overall and by type of patient (prevalent/incident), by type of diagnosis (time between the first medical events related to GCA and diagnosis to GCA as qualitative variable in 3 classes early/in standard time/late diagnosis), and by type of physicians who follows the patient.

- Initial presentation:
 - Proportion of patients with at least one cranial manifestation at diagnosis and the proportion of each symptom of this family (Headaches/ Scalp sensitivity / Anomalies of the temporal arteries (temporal artery sensitivity or decreased pulsation) / Ischemia-related vision impairment and-or loss / Mouth pain or jaw claudication during mastication / Stroke or transient ischemic attack (TIA) / Other)

Listing of Ischemia-related vision impairment / loss and other cranial manifestation at diagnosis will be presented.

- Proportion of patients with at least one PMR symptom at diagnosis and the proportion of each symptom of this family (Morning stiffness and-or pain in the shoulder girdle/ Morning stiffness and-or pains in the pelvic girdle/ Inflammatory arthromyalgia/ Peripheral arthritis/ Other)

A listing of other PMR symptom will be presented.

- Proportion of patients with at least one extracranial event (excluding PMR) at diagnosis and the proportion of each symptom of this family (Thoracic or abdominal aortic aneurysm and-or dilatation/ Aortitis and-or involvement of aortic branch(s) in imaging/ Angina and-or Myocardial infraction/ Claudication of an upper limb and-or claudication of a lower limb/ Sign of subclavian stenosis (asymmetry of pulse, blood pressure, subclavian murmur)/ Other)

A listing of other extracranial events (excluding PMR) will be presented.

- Value of ESR (mm/1st h) and CRP (mg/L) at diagnosis and at inclusion.
- Proportion of patients having abnormal value of ESR (ESR $>$ 50 mm/h)/CRP (CRP $>$ 25 mg/L) at diagnosis
- Proportion of patients having abnormal value of ESR (ESR $>$ 50 mm/h)/CRP CRP $>$ 25 mg/L) at inclusion

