- Proportion of patients with at least one general sign at diagnosis and the proportion of each sign (fever $>$ 38°C with no other etiology than GCA, weight loss and its value (%), alteration of the general condition)

For the value of ESR and CRP at diagnosis, only value measured in the previous month, the current month and the month following the date of diagnosis will be considered. For values at inclusion, only measures done within 6 month before the date of inclusion will be considered.

A listing of other initial characteristics related to GCA at diagnosis will be presented.

- Clinical form:
 - Proportion of patients with at least one relapse
 - In patient with at least one relapse:
 - Number of relapses per patient
 - Time between first relapse and diagnosis (months) ([APPENDIX](#))
 - Mean time between 2 consecutive relapses (months) ([APPENDIX](#))
 - The following information will be summarized by relapse:
 - Proportion of used criteria to assess relapse (Clinical/ Biological/ Imagery/ Other)
 - Proportion of patients using GCs just before the relapse
 - GCs dose at relapse diagnosis (mg/day)
 - Proportion of relapses of patients with Immunosuppressants just before the relapse
 - Proportion of relapses of patients with Targeted biologic therapy just before the relapse
 - Proportion of relapses of patients using other treatments just before the relapse
 - Proportion of relapses for which Glucocorticoids (GCs) were used as medical care for the relapse
 - GCs dose used for relapse medical care (mg/day)
 - Proportion of relapses for which Immunosuppressants were used as medical care for the relapse
 - Proportion of relapses for which Targeted biologic were used as medical care for relapse
 - Proportion of relapses for which other GCA (HORTON) treatments were used as medical care for relapse.
 - Distribution of GCs dependence
 - Current dose at inclusion (mg/day)
 - Number of kinetics per patient since diagnosis
 - Time between first kinetic and diagnosis (months) ([APPENDIX](#))
 - Proportion of patients with at least one kinetic ongoing at inclusion
 - Mean time between 2 consecutive kinetics (months) ([APPENDIX](#))
 - Total cumulative GCs dose according to investigator (excluding IV bolus) since diagnosis (mg) ([APPENDIX](#))
 - The following information will be summarized by Kinetic:
 - Kinetic duration (months) ([APPENDIX](#))
 - Proportion of kinetics with IV initial administration (bolus) (Yes/No)
 - If yes, total number of days

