 - IV bolus dose (mg)
 - Switch PO dose (mg/day)
 - Cumulative dose according to investigator (mg)
 - Proportion of kinetics for which a corticotherapy for GCA (Horton) care has restarted after the kinetic
 - Proportion of patients with at least one GCA complication
 - Proportion of patients with ongoing specific treatment(s) for GCA complications

Current and/or past GCA complications according to the investigator judgment will be coded using the medical dictionary MedDRA®. They will be described by SOC and PT overall and by type of physicians who follows the patient.

To determine the potential factors associated to relapse, a logistic regression will be used. The outcome variable will be relapse (Yes/ No). First, a univariate analysis will be conducted. All significant

factor at the 20% threshold will be selected for a multivariate analysis. A backward elimination procedure will be used with a threshold of 5%.

The associated factors that will be studied are:

- Age (in classes)
- Gender (Male/Female)
- BMI at diagnosis (in classes)
- Smoking status (Smoker/ Former smoker/ Non-smoker ever / Unknown)
- Type of patient (Prevalent or incident)
- Physician who referred the patient (General practitioner/ Ophthalmologist / Neurologist/ Emergency/ Internist/ Rheumatologist/Other),
- Patient considered with late diagnosis by the physician who referred him (Yes/ No)
- Patient considered with late diagnosis according to calculated time interval between the first medical events related to GCA and diagnosis : (Yes/No)
- Patient with at least one cranial GCA symptom at diagnosis (Yes/No),
- Patients with at least one PMR symptom at diagnosis (Yes/No),
- Patient with at least one extracranial GCA symptom at diagnosis (Yes/No),
- Patient with abnormal value of ESR at diagnosis (ESR>50 mm/h)
- Patient with abnormal value of CRP at diagnosis (CRP> 25 mg/L) (Yes/No),
- Patient with fever (>38°C) at diagnosis (Yes/No),
- Patient with weight loss at diagnosis (Yes/No),
- Patient with alteration of the general condition at diagnosis (Yes/No),
- Patient has taken at least one immunosuppressant since diagnosis (Yes/No)
- Patient has taken at least one targeted biological therapy since diagnosis (Yes/No)
- Patient has taken at least one other long-term treatment for the medical care of GCA since diagnosis (Yes/No)
- VAS score (global arteritis activity) by patient (>50mm/≤50mm)
- VAS score (global arteritis activity) by physician (>50mm/≤50mm)
- Cumulative dose of GCs (mg)

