- Patient with alteration of the general condition at diagnosis (Yes/No),
- Number of relapses
- Patient has taken at least one immunosuppressants since diagnosis (Yes/No)
- Patient has taken at least one targeted biological therapy since diagnosis (Yes/No)
- Patient has taken at least one other long-term treatment for the medical care of GCA since diagnosis (Yes/No)
- Patient considered with late diagnosis according to calculated time interval between the first medical events related to GCA and diagnosis (Yes/No)
- Cumulative dose of GCs

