8 STATISTICAL APPENDICES

APPENDIX (Derived data)

The following derived data will be calculated and included in the listings:

(1) **Enrollment duration**

Enrollment duration (days) = date of inclusion of the last patient – date of inclusion of the first patient

(2) **Time between first medical events related to GCA and diagnosis**

For prevalent patients (not newly diagnosed):

Time between first medical events related to GCA and diagnosis (months) = date of diagnosis – date of first medical events related to GCA

For incident patient (newly diagnosed):

Time between first medical events related to GCA and diagnosis (months) = date of diagnosis (in MM/YY format) – date of first medical events related to GCA

The date of diagnosis which is in format (DD/MM/YYYY) will be transformed into (MM/YYYY)

(3) **Time between diagnosis and inclusion**

For prevalent patients:

Time between diagnosis and inclusion (months) = (date of inclusion – date of diagnosis)/30.4375

If the date of diagnosis in format (DD/MM/YYYY) is not completed, the diagnosis date in format (MM/YYYY) will be used and the inclusion date will be transformed into (MM/YYYY).

For incident patients:

Time between diagnosis and inclusion (months) = (date of inclusion – date of diagnosis)/30.4375

The date of diagnosis in format (DD/MM/YYYY) will be used.

(4) **Duration of treatment taken**

Duration of treatment taken (months) = End date – start date +1

if ongoing treatment at inclusion:

Duration of treatment taken = Date of inclusion – start date +1

For this calculation, the date of inclusion which is in format (DD/MM/YYYY) will be transformed into (MM/YYYY) as the start date of treatment.

(5) **Time between first relapse and diagnosis**

Time between first relapse and diagnosis (months) = date of first relapse after diagnosis – date of diagnosis.

For this calculation, the date of diagnosis (for incident patient) which is in format (DD/MM/YYYY) will be transformed into (MM/YYYY) as the date of relapse.

(6) Mean time between 2 consecutive relapses

Time between 2 consecutive relapses (months) = [date of relapse (i+1) – date of relapse (i)]/(Total number of relapses per patient-1)

(7) Time between first kinetic and diagnosis

Time between first kinetic and diagnosis (months) = date of initiation of first kinetic – date of diagnosis

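### Factors associated with relapse are analysed only as any versus none, although relapse counts, relapse dates and time since diagnosis are all available

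*SAP*

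**What the plan says.** Protocol 7.2.3.2 states: "Analysis of potential factors associated to relapse will be performed using logistic regression". It leaves the factors to the SAP. SAP 5.5.2 fixes the outcome: "The outcome variable will be relapse (Yes/ No". Tables 22 and 23 carry it as at least one relapse against none, with univariate screening at 20% and backward elimination at 5%.

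The data collected are richer:

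- **Dates.** Protocol 5.3.1 records for the clinical form "Relapses: date (month, year), treatments and doses, criteria for identifying relapse (clinical, biological, other".
- **Counts.** Protocol 7.2.3.2 lists "Proportion of patients with relapse and number of relapse" as an endpoint, and SAP 5.5.2 describes "Number of relapses per patient". The count also appears as a candidate factor ("Number of relapses") in the separate model for GCA activity.
- **Timing.** The SAP appendix of derived data defines "Time between first relapse and diagnosis (months) = date of first relapse after diagnosis – date of diagnosis", used for description only.
- **Time at risk.** SAP 5.5.2 says "Time between diagnosis and inclusion will be described as quantitative variable (months". That variable is not among the candidate factors for relapse. The only related candidate is incident versus prevalent, split at 6 weeks.

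Neither document gives a reason for using the binary outcome alone.

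**The concern.** A patient diagnosed two months ago and one diagnosed eight years ago are both prevalent, and the planned model treats their time at risk as equal. One relapse in eight years also counts the same as five in three. As time since diagnosis lengthens, most patients will have relapsed at least once. The binary outcome then saturates, while the count continues to separate patients.

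Adding time since diagnosis to the logistic model would deal with unequal time at risk, but it would not recover the information in the count. What is at stake is the list of factors that survives in Table 23: with about 300 patients, real factors may be dropped that the collected data could have shown.

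**Working it through.** **Plan's own figure.** There is none to reproduce. Protocol 7.1.1 declares a sample-size rationale not applicable, and no power, relapse rate or effect size is given for this analysis.

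**Inputs from the documents.** n = 300 (Protocol 3.1). Two-sided 5%, taken from the SAP's elimination threshold. Incident means up to 6 weeks from diagnosis. Time since diagnosis has mean 3.7 and SD 2.6 years, which is the follow-up of the EGB cohort (Protocol section 1), used as a proxy.

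**Assumptions, not in the documents.** 15% incident, with times spread evenly over 0-6 weeks. Factor present in 40% (120 with, 180 without). Rate ratio 1.5 on every relapse. 0.2 relapses per year without the factor, hence 0.3 with it. Overdispersion k = 0 or 1.

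**Time at risk.** A gamma distribution has shape (3.7/2.6)² = 2.025 and scale 2.6²/3.7 = 1.827. Overall mean = 0.85 × 3.7 + 0.15 × 0.058 = 3.154 years.

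**Any versus none, no time term, k = 0.** For prevalent patients P(at least one) = 1 − (1 + rate × 1.827)^(−2.025), which is 0.468 at 0.2 and 0.587 at 0.3 per year. For incident patients it is 0.011 and 0.017. Mixing:

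- without the factor: 0.85 × 0.468 + 0.15 × 0.011 = 0.399
- with the factor: 0.85 × 0.587 + 0.15 × 0.017 = 0.502

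The difference is 0.102. The pooled proportion is 0.440, so SE = √(0.440 × 0.560 × (1/180 + 1/120)) = 0.0585; the unpooled SE is 0.0584. Power = Φ((0.102 − 1.96 × 0.0585)/0.0584) = Φ(−0.21) = 42%.

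**Rate model, k = 0.** Expected relapses are 180 × 0.2 × 3.154 = 113.5 and 120 × 0.3 × 3.154 = 113.5. SE(log rate ratio) = √(2/113.5) = 0.133. z = ln(1.5)/0.133 = 3.05. Power = Φ(3.05 − 1.96) = 86%.

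**Both models, k = 1.** The rate-model information per patient is the mean of μ/(1 + μ), where μ = rate × time. Integrated numerically this is 0.326 and 0.401, giving 180 × 0.326 = 58.6 and 120 × 0.401 = 48.1. SE = √(1/58.6 + 1/48.1) = 0.195, z = 2.08, power = Φ(0.12) = 55%. The any-versus-none probabilities are also 0.326 and 0.401, since 1 − 1/(1 + μ) is the same quantity, and power is 27%.

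**Time-adjusted logistic, by simulation.** Two independent sets of 500-600 datasets per setting, same assumptions. Where one value is shown, it comes from one set.

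| Mean years since diagnosis | Relapses/year | k | Logistic, no time term | Logistic + log time | Negative binomial, log-time offset |
|---|---|---|---|---|---|
| 3.7 | 0.2 | 0 | 44% | 53-55% | 84-86% |
| 3.7 | 0.2 | 1 | 28% | 32-33% | 58-60% |
| 3.7 | 0.5 | 0 | 32% | 55% | 99% or more |
| 3.7 | 0.5 | 1 | 23% | 27-31% | 73-76% |
| 1.5 | 0.2 | 0 | 30% | 38% | 46% |
| 1.5 | 0.2 | 1 | 23% | 26% | 37% |

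With no true effect the rate model rejected in 2-7% of datasets. At the shorter duration the gain over time-adjusted logistic is 46 − 38 = 8 and 37 − 26 = 11 points.

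**How far the size moves.** Over 2160 combinations of rate, effect, dispersion, prevalence, duration and incident share, the rate model's gain over unadjusted any-versus-none ran from −1 to 90 points, with median 22; a quarter of combinations were below 10. At the SAP's 20% screening threshold a narrower grid gave about 4 to 47 points. If the relapse rate falls to 30% of its initial level after two years, the loss is about 15 to 26 points. If the factor acts only on the first relapse, the order reverses: logistic 43-60% against 26-42% for a Poisson rate model with robust errors.

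**The case against.** The strongest reply has four parts.

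1. **The protocol names logistic regression for relapse, and the SAP implements it.** Neither document says that relapse frequency is the question, so a count model changes the quantity estimated. This stands, and it is why the logistic model should be kept. A reader might infer that the planned analysis answers the wrong clinical question; the documents do not support that.

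2. **The power figures assume what favours the rate model.** The simulated counts have a constant rate and an equal effect on every relapse. Treatment may change after a first relapse, so an effect confined to the first relapse is plausible, and then logistic regression does better. This stands. A reader might take the example as a fixed loss built into the plan, but the relapse rate, dispersion and effect size are all assumed.

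3. **The 3.7-year proxy may be too long.** It is follow-up in a claims cohort, whereas this study enrols patients starting or under treatment. The same cohort's first glucocorticoid sequence averaged 17.2 months, which is nearer the 1.5-year rows, where the gain is modest. This stands as a caution on size.

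4. **The analysis is exploratory, in a descriptive study, and nothing is lost because Table 16 reports counts and timing.** Only partly. The loss is indeed confined to Tables 22-23. But Protocol 7.2.1 says no testing will be done, while the SAP keeps or drops factors by p-value. Once significance decides what is reported, power matters.

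**Conclusion.** The point holds in a limited form. The relapse-factor analysis uses any versus none alone, although counts and dates are collected, and it has no term for time since diagnosis beyond the 6-week split. The missing time term is the firmer part, because it does not depend on the assumed rates.

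The cost in power is conditional. With an effect on the relapse rate throughout follow-up and the EGB proxy at 0.2 relapses per year, it is roughly 30 points without overdispersion and 25 with strong overdispersion, measured against a time-adjusted logistic model. It is smaller with low rates or short duration, and it reverses if a factor affects only the first relapse. This supports adding a model, not replacing the protocol's. It should be corrected, but it concerns an exploratory part of a secondary objective and does not touch the primary description.

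**What to change.** In SAP 5.5.2 and Tables 22-23:

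- Keep the protocol's logistic model and add time since diagnosis as a covariate.
- Alongside it, add a negative binomial regression of the number of relapses since diagnosis, with log(time since diagnosis) as offset, reporting rate ratios with 95% CI.
- Set a minimum time, for example half a day or half a month. The SAP's formula gives zero for a patient included on the day of diagnosis, and the logarithm is then undefined.
- Declare the addition and the covariate in SAP 5.6.

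State the limits with the results. The rate model assumes a roughly constant relapse rate and an equal effect on first and later relapses. Neither model removes reverse causation for treatments taken since diagnosis, cumulative glucocorticoid dose or VAS at inclusion, each of which may follow from relapse.

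The cost is SAP wording, one extra model call (PROC GENMOD) and added table columns, with no new data or visits. Readers will see rate ratios beside odds ratios; if the two disagree, an effect limited to first relapses is one explanation to consider.

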7.2 Statistical analyses

The analysis will be performed by ITEC Services in accordance with this section and with the Statistical Analysis Plan (SAP) that supplements it.

7.2.1 *General statistical methods*

The statistical analysis will be performed using SAS® software, version 9.3 or upper.

A SAP describing the planned statistical analysis in detail with Tables, Figures and Listings (TFLs) templates will be developed as a separate document. This SAP will be finalised and validated before each database freeze by CPF.

The descriptive summary statistics will be:

- » for quantitative parameters: mean, standard deviation, median, first and third quartiles, minimum and maximum, filled and missing data;
- » for qualitative parameters: frequency, percentage per modality, filled and missing data

As this is a descriptive study, no statistical testing will be performed. However, 2 sided 95% confidence intervals will be calculated for every relevant proportion / mean.

7.2.2 *Study populations*

Three populations will be defined for the analyses:

- » Population of Physicians: all the specialists who have included at least one patient meeting the eligibility criteria for the study
- » Total Population: all included patients
- » Analysis Population: all included patients meeting the inclusion and non-inclusion criteria

The number of potential exclusions from the patient population used for analysis and the reasons for these exclusions will be described. The patient disposition will be described.

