- GCA activity

- Scores of the physician global arteritis activity VAS will be analysed as quantitative variables and in classes (≤ 50 ; > 50 mm).
- Scores of the patient global arteritis activity VAS will be analysed as quantitative variables and in classes (≤ 50 ; > 50 mm).

The VAS scores of physician and patient will be divided into classes. The same cut-off (≤ 50 ; > 50 mm) for the two scores will be defined by CHUGAI according to their medical relevance.

In this case, the concordance between the scores of the patient and physician global arteritis activity VAS will be evaluated using the kappa K coefficient, which will be interpreted as follows:

- $K < 0.0$: No match
- $0.0 \leq K \leq 0.2$: Poor agreement
- $0.2 < K \leq 0.4$: Fair agreement
- $0.4 < K \leq 0.6$: Moderate agreement
- $0.6 < K \leq 0.8$: Good agreement
- $K > 0.8$: Very good agreement

To evaluate the GCA activity, the score of the physician global arteritis activity VAS will be used. For this score a threshold value = 10 mm was defined and validated by CHUGAI.

Patients with physician's VAS score less than or equal to 10 mm will be considered with "non-active GCA", while patients with physician's VAS score greater than 10 mm will be considered with "active GCA".

In this case, the potential associated factors with the increase of the GCA activity will be studied by logistic regression.

The outcome variable will be GCA (active/ Non-active). First, a univariate analysis will be conducted. All significant factor at the 20% threshold will be selected for a multivariate analysis. A backward elimination procedure will be used with a threshold of 5%.

The associated factors that will be studied are:

- Age (in classes)
- Gender (Male/Female)
- BMI at diagnosis (in classes)
- Smoking status (Smoker/ Former smoker/ never smoker/unknown)
- Prevalent or incident patient,
- Physician who referred the patient,
- Patient considered with late diagnosis by the physician who referred him (Yes/ No)
- Patient with at least one cranial GCA symptom at diagnosis (Yes/No),
- Patients with at least one PMR symptom at diagnosis (Yes/No),
- Patient with at least one extracranial GCA symptom at diagnosis (Yes/No),
- Patient with abnormal value of ESR (ESR>50 mm/h) at diagnosis
- Patient with abnormal value of CRP (CRP> 25 mg/L) at diagnosis (Yes/No),
- Patient with fever at diagnosis (Yes/No),
- Patient with weight loss at diagnosis (Yes/No),

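### The relapse and activity models are selected by p-value, then reported with ordinary odds ratios, 95% CIs and p-values that ignore the selection

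*SAP*

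**What the plan says.** For relapse, "The outcome variable will be relapse (Yes/ No"), SAP 5.5.2 lists its candidates under "The associated factors that will be studied are". The list has 22 entries, from age to cumulative glucocorticoid dose. Each is tested alone; then every significant "factor at the 20% threshold will be selected for a multivariate analysis. A backward elimination procedure will be used with a threshold of 5" per cent.

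The activity model repeats the rule: "The outcome variable will be GCA (active/ Non-active). First, a univariate analysis will be conducted", followed by the same two thresholds. Its list has 21 entries; the Table 26 shell omits the number of relapses and so shows 20.

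Tables 23 and 27 have two pairs of columns, one for the complete model and one for the model after backward elimination, each with odds ratio, 95% CI and p-value. By its footnote the complete model contains only factors that passed the 20% screen. Neither the analysis sections nor the table shells mention adjustment for multiplicity, shrinkage, resampling or validation.

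Protocol 7.2.1 states: "As this is a descriptive study, no statistical testing will be performed". Protocol 7.2.3.2 nevertheless plans a logistic regression for relapse and leaves its factors to the SAP.

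**The concern.** A factor stays in the final model only if its estimate is far enough from zero in this sample. Among factors with a modest true association, those that survive are the ones whose estimates chance pushed outward. Their odds ratios are therefore too extreme on average. Their intervals, calculated as if the model had been fixed in advance, cover the truth less often than 95%.

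For a single-parameter factor with no association the consequence is absolute. It survives only if its Wald p-value is at or below 5%, so its printed interval excludes 1 whenever it is printed, and conditional coverage is essentially zero.

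A second, distinct issue is the number of candidates: about twenty factors per model are read at 5%, so some will appear by chance. The candidates include immunosuppressant and targeted biologic use, so a chance survivor could be read as a treatment linked to relapse or activity.

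**Working it through.** The documents state no error rate, relapse rate or sample-size calculation for these models, so there is no figure to reproduce.

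**Inputs from the documents**
- N = 300 (SAP 3.5.1); thresholds 20% and 5% (SAP 5.5.2).
- Relapse model: 22 factors. BMI has 4 classes (3 parameters). "Smoking status (Smoker/ Former smoker/ Non-smoker ever / Unknown") has 4 levels (3 parameters). Referring physician has 7 levels (6 parameters). The other 19 take one each if cumulative dose is continuous: 19 + 3 + 3 + 6 = 31.
- Activity model: 21 factors, 30 parameters.

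**Assumed inputs:** outcome rate (35% below, 20% to 50% in the ranges), factor prevalences and correlations.

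**1. Effect of selection on a surviving odds ratio: hand check**

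Take a binary factor with 50% prevalence and a 35% outcome rate, and ignore the other factors.
- SE(log OR) ≈ 1/√(300 × 0.35 × 0.65 × 0.25) = 1/√17.06 = 0.242.
- Survival at 5% needs |log OR estimate| > 1.96 × 0.242 = 0.474, that is, an estimated odds ratio above 1.61 or below 0.62.

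True OR 1.2 (log 0.182):
- Upper cut: a = (0.474 − 0.182)/0.242 = 1.207, tail 0.1137. Lower cut: b = (−0.474 − 0.182)/0.242 = −2.713, tail 0.0033. P(survive) = 0.117.
- Mean log OR if it survives = 0.182 + 0.242 × [φ(1.207) − φ(2.713)]/0.117 = 0.182 + 0.242 × (0.193 − 0.010)/0.117 = 0.56, so OR ≈ 1.75.
- The interval covers the truth only when the estimate lies above the upper cut but within 0.474 of the truth: (0.1137 − 0.025)/0.117 = 76%.

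True OR 1.5 (log 0.405):
- a = (0.474 − 0.405)/0.242 = 0.285, tail 0.388; the lower tail is negligible.
- Mean log OR if it survives = 0.405 + 0.242 × 0.383/0.388 = 0.644, so OR ≈ 1.90. Coverage = (0.388 − 0.025)/0.388 = 94%.

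**2. The same quantities under the full SAP rule, by simulation**

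One real factor, 21 null factors, 300 patients, 35% outcome rate:

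| True OR | Mean OR when retained | Coverage of the printed 95% CI |
|---|---|---|
| 1.2 | about 1.8 | 68% and 73% in two separate runs |
| 1.5 | about 1.96 | 91% to 94% |

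The hand check and the simulation agree closely.

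**3. Multiplicity**
- Expected false factors at 5%, if all 22 are null: 22 × 0.05 = 1.1.
- P(at least one), independent tests: 1 − 0.95^22 = 67.6%; with 21 factors 65.9%; with 20 factors 64.2%.
- Factors expected to pass the 20% screen under the null: 22 × 0.20 = 4.4, so the screen gives almost no protection.
- Simulated SAP rule, nothing associated (1,500 runs per scenario, Monte Carlo SE about 0.012): at least one survivor in 62% to 67% of studies for relapse, with 0.99 to 1.15 false factors on average, and in 62% to 65% for activity. The scenarios covered outcome rates of 20% to 50%, common correlation up to 0.5, 5% missing per factor, and N = 200.
- Comparator: one fixed 22-factor model with no selection, read at 5%, gave at least one false factor in about 71% to 75% of simulated studies.

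**The case against.** The strongest reply is that the two-in-three figure does not measure the harm done by selection. That is correct. A reader might infer that the 20%/5% rule causes it, but an unselected model read at 5% gives at least as high a rate. The figure is multiplicity; selection shows in the inflated odds ratios and lost coverage. Nor does it mean that two thirds of reported factors are false: it is the chance of one or more when nothing is associated.

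That null state is also unlikely here. Incident patients have had at most six weeks since diagnosis in which to relapse, and the SAP records immunosuppressants and biologics as care for relapse, so some associations are built in. About one false factor per model is the more useful figure.

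Three further inferences go beyond the documents:
- *The SAP breaches the protocol's no-testing statement.* The protocol itself plans the relapse regression and says that activity factors will be studied. This is a minor tension within the protocol.
- *There are too few events per parameter.* At 35% there are 105 events, but dividing by all 31 candidates describes no model that the screen would normally yield. Under the null about 4.3 factors (5.6 to 5.9 parameters) pass, or about 105/5.8 = 18 events per parameter.
- *The two models' error rates can be multiplied together.* They share patients, and each uses information from the other's outcome, so independence cannot be assumed.

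In mitigation, the candidates are listed in advance, the SAP speaks of potential factors, the analyses are secondary, and univariate, complete and reduced results are all tabulated. This makes the selection visible but does not correct the final columns. The complete model, limited to screened factors, is itself post-selection.

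**Conclusion.** The point holds and should be addressed. The odds ratios, 95% CIs and p-values planned for the backward-elimination columns of Tables 23 and 27 do not have their nominal meaning. The distortion is large for weak associations (1.2 reported as about 1.8, coverage roughly 70%) and modest for moderate ones (1.5 reported as about 1.96, coverage 91% to 94%). Separately, multiplicity leaves about one false factor per model.

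The odds-ratio figures assume 300 complete records, a 35% outcome rate, a factor with 50% prevalence and independent factors; the documents supply only the 300. The multiplicity figures changed little over the range tried. Very strong overlap between candidates, such as ESR with CRP or the two late-diagnosis variables, would lower them somewhat. The primary objective is unaffected.

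**What to change.** Keep the listed candidates and the planned selection, and in SAP 5.5.2:
- label both models exploratory;
- bootstrap the whole procedure, repeating the 20% screen and the 5% elimination in each resample (for example 1,000 resamples);
- report each factor's inclusion frequency and shrunken odds ratios;
- remove the nominal p-values and 95% CIs from the backward-elimination columns of Tables 23 and 27 or, at the least, footnote that they ignore selection and multiplicity. The complete-model columns need the same footnote, because the screen has already acted on them.

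A single penalised model without selection, for example on factors known at diagnosis, is an optional addition. It addresses a different question and would not by itself lower the false-positive rate if read at 5%.

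The cost is some SAS programming and SAP wording, with no new data or visits. The downside is that fewer factors will be called associated.
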